### **5.6.5 Adverse Events of Focus (AEOF)**

Rozanolixizumab treatment-emergent adverse events of focus (AEOF) include the following categories:

- Headaches
- Possible aseptic meningitis
- Gastrointestinal disturbances

- Hypersensitivity reactions
- Anaphylactic reactions
- Injection site reaction
- Infections
- Opportunistic infections
- Effects on the kidney
- Drug related hepatic disorders
- Effect on lipids

Further details are described in [Section 8.3](#).

A by-participant listing of all treatment-emergent AEOF by category (as listed above) will be provided. The number and percentage of study participants who experience each treatment-emergent AEOF will be summarized by treatment period and treatment group based on the SS-t.

The following tables will be presented:

- Incidence of each AEOFs by SOC, High Level Group Term (HLGT), HLT and PT
- Incidence of each Serious AEOFs by SOC, High Level Group Term (HLGT), HLT and PT
- Incidence of each AEOFs by relationship, SOC, HLT, HLT and PT
- Incidence of each AEOFs by maximum intensity, SOC, HLT, HLT and PT

Note that each of the AEOF categories will be tabulated independently, eg, for the overall incidence summary, there will be one page showing the incidence of headaches, one page showing incidence of gastrointestinal disturbances, one for hypersensitivity reactions, etc.

### **5.6.6 Clinical Laboratory Evaluations**

All laboratory results values (clinical chemistry and hematology) will be listed by study participant, planned treatment sequence, time point and parameter. Changes from Baseline for numeric variables, the reference ranges and a flag to indicate whether values are below the lower limit of the reference range or above the upper limit of the reference range will be presented.

Separate listings of all clinical chemistry and hematology laboratory results for participants who had at least one treatment-emergent marked abnormality (as defined in the abnormality criteria in [Section 8.1.1](#)) during the study will be presented.

Urinalysis results will be listed for all study participants by treatment sequence, and will include changes from Baseline for numeric variables, and the reference ranges (if applicable).

Any additional laboratory variables which were not collected for screening eligibility and are not included in the outputs described previously will be listed separately for all time points collected. These will include the following:

- Serology
- Serum pregnancy test (for women of childbearing potential, if taken post screening)

- Urine pregnancy tests
- Urine toxicology screen (if taken post screening)
- IGRA assessments
- COVID-19 testing (for participants enrolled under Protocol Amendments 1 and 2 only)

Clinical chemistry and hematology parameters will be summarized by planned treatment sequence and periods and time point for both absolute values and changes from Baseline. Summaries will be based on the SS-r.

Treatment-emergent marked abnormalities with abnormalities defined in Appendix 1 [Section 8.1.1](#) will be summarized by clinical chemistry and hematology groups, planned treatment sequence and visit. Treatment-emergent here refers to measurements obtained on or after the date of the first dose of IMP in Run-In, and on or before the earliest date of the following: the last infusion (including Run-Out if applicable) +56 days, final contact date, or death, and which did not meet the abnormality criteria at Baseline.

Measurements that are below the limit of quantification (BLQ) or above the limit of quantification (ALQ) will be presented as received in the listings. For the purpose of calculating change from baseline or for descriptive statistics, BLQ values will be imputed with half of the lower limit of quantification (LLOQ) and ALQ values will be imputed to the upper quantification limit (ULOQ).

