In MG0003, a Phase 3 study evaluating efficacy and safety of sc rozanolixizumab in adult patients with gMG █ clinical efficacy of rozanolixizumab was demonstrated by improvements vs placebo in all efficacy endpoints tested in the study. There were clinically meaningful and statistically significant reductions from baseline in the primary endpoint, MG activities of daily living (ADL) score, at Day 43 for both rozanolixizumab dose groups versus placebo.

The identified adverse drug reactions associated with sc administration of rozanolixizumab are headaches, diarrhoea, pyrexia, nausea, upper respiratory tract infections, arthralgia, rash, injection site reactions, vomiting, myalgia, and herpes simplex infections.

Headache is the most commonly reported ADR, and these were mostly mild to moderate and easily managed with over-the-counter medications. Important potential risks are serious hypersensitivity reactions and serious infections. Other safety topics of interest include effects on vaccination response, effects on the kidney, reductions in albumin and plasma proteins, drug-induced aseptic meningitis, and decreased platelet counts. These risks can be mitigated by careful monitoring, exclusion of at-risk study participants, and appropriate protocol withdrawal

and stopping criteria. Additionally, protocol guidance for management of hypogammaglobulinemia/infection and infusion and hypersensitivity reactions is provided in Appendix 14 (Section 10.14) and Appendix 15 (Section 10.15), respectively. The management of and expedited reporting requirements of the AESMs (severe and/or serious headaches and suspected aseptic meningitis) to UCB are specified in Appendix 13 (Section 10.13).

Restrictions on use of live vaccines have been defined in the exclusion criterion 25a. If vaccination with non-live vaccines (including coronavirus disease 2019 [COVID-19] vaccines) is considered necessary once a study participant has started therapy with IMP, then the degree of protection afforded with a vaccine may be compromised while the participant is being treated with IMP.

Given the clinical evidence to date, the overall risk to the participants in this study is deemed to be low and the benefit-risk balance for study participants is anticipated to be favorable.

More detailed information about the known and expected benefits and risks and reasonably expected adverse events (AEs) of rozanolixizumab may be found in the current version of the IB.

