9.4 Planned safety and other analyses

9.4.1 Safety analyses

All safety variables will be analyzed by descriptive methods and presented by sequence and by period (Period 1, Period 2, or SFU) showing the treatment when the safety event occurred. In addition, events will be summarized by treatment and period. Any events in the SFU Period from sequence 1 and 2 will be tabulated under active treatment.

- Frequency and intensity of TEAEs from Baseline to SFU, and
- TEAEs leading to withdrawal of IMP

will be the safety variables analyzed in this study and will be included in the summary tables.

The overall frequency during the study period will be presented for each of the safety variables, as well as separately by System Organ Class, high level term, and preferred term (Medical Dictionary for Regulatory Activities [MedDRA®]). The data will be displayed as number of

study participants experiencing the event, percentage of study participants, and number of events. Additional tables will summarize the safety variables by maximum intensity, by intensity, and by relationship to study drug.

Laboratory evaluations and vital signs will be analyzed over time. Possibly clinically significant treatment-emergent abnormalities will be listed and summarized by visit for each treatment group.

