**Table 1-1: Objectives and Estimands/Endpoints**

Objectives	Endpoints/Estimands
	

Population level summary: mean difference in average BPI-SF interference score between the two treatments

Secondary	

To assess the safety and tolerability of rozanolixizumab in study participants with severe FMS

To evaluate the efficacy of rozanolixizumab for treatment of study participants with severe FMS

	

Occurrence of TEAEs during the study

TEAEs leading to withdrawal of IMP

BPI-SF average interference score after 24 weeks of treatment

FIQR score after 10 weeks of treatment

Mean 7-day average daily pain score (Pain NRS) after 12 weeks of treatment

Mean 7-day fatigue score (Fatigue NRS) after 12 weeks of treatment

Exploratory	

To assess the PK of rozanolixizumab in study participants with severe FMS

To evaluate the efficacy of rozanolixizumab for treatment of study participants with severe FMS

To assess the safety and tolerability of rozanolixizumab in study participants with severe FMS

To evaluate the incidence and emergence of ADA of rozanolixizumab in study participants with severe FMS

To assess the PD effect of rozanolixizumab in study participants with severe FMS

To assess the effect of rozanolixizumab on exploratory biomarkers in study participants with severe FMS

	

Plasma concentration of rozanolixizumab prior to dosing on Week 13 and Week 25

Pressure pain threshold as measured by pressure algometry

Change from Baseline in vital signs and laboratory results at scheduled assessments during the Treatment Period through the Run-Out Period

Antidrug antibody incidence at scheduled assessments during the Treatment Period

Value (absolute) and change from Baseline (absolute and percentage) in serum total IgG and IgG subclasses at scheduled assessments during the Treatment Period

Assessment of IgG binding in in vitro cell assay at scheduled assessments during the Treatment Period and the Run-Out Period

Assess genetic variation for potential effects on disease progression and/or drug

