#### Chemistry

PARAMETER	UNIT (conventional)	UNIT (standard)	MARKED ABNORMALITY CRITERIA
AST (SGOT)	U/L	U/L	>5.0 x ULN
ALT (SGPT)	U/L	U/L	>5.0 x ULN
ALP (Alkaline Phosphatase)	U/L	U/L	>5.0 x ULN
Bilirubin (Total)	mg/dL	umol/L	>3.0 x ULN if Baseline value is normal (based on reference range); >3.0 x Baseline value if Baseline is abnormal
Albumin 	g/dL	g/L	<2 g/dL; <20 g/L
Creatinine	mg/dL	umol/L	>3.0 x ULN or >3.0 x  Baseline
Estimated glomerular filtrate rate (eGFR)	mL/min/1.73 m 	mL/min/1.73 m 	eGFR ≤29 mL/min/1.73 m 

PARAMETER	UNIT (conventional)	UNIT (standard)	MARKED ABNORMALITY CRITERIA
C reactive protein (CRP) 	mg/L	mg/L	>10 mg/dL; >100mg/L
Calcium	mg/dL	mmol/L	Low: Corrected serum calcium of <7.0 mg/dL; <1.75 mmol/L
			High: Corrected serum calcium of >12.5 mg/dL; >3.1 mmol/L
Immunoglobulin G	(g/L)	(g/L)	<1.09 g/L (BLQ)
Potassium	mmol/L	mmol/L	Low: <3.0 mmol/L
			High: >6.0 mmol/L
Sodium	mmol/L	mmol/L	Low: <125 mmol/L
			High: >155 mmol/L
Glucose 	mg/dL	mmol/L	Low: <40 mg/dL; <2.2 mmol/L
			High: > 250 mg/dL; >13.9 mmol/L
Total Cholesterol	mg/dL	mmol/L	>400 /dL; >10.34 mmol/L
Triglycerides	mg/dL	mmol/L	>500 mg/dL; >5.7 mmol/L

Abbreviations: ALT= alanine aminotransferase; AST = aspartate aminotransferase; dL = deciliter; GGT: gamma-glutamyltransferase; L = liter; mg = milligram; mmol = millimoles;  $\mu$ g = microgram; U = unit; ULN = upper limit of normal

Note: Marked abnormality criteria are defined by Grade 3 or higher events according to the Common Terminology for Adverse Events (CTCAE), Version 5.0, November 17, 2017 unless otherwise noted.

WBC (Leukocytes) markedly abnormal high criterion is not based on Version 5 CTCAE Grade 3 or higher criteria. Due to the allowance of concomitant steroid medication that by its mechanism of action may elevate WBCs, the safety alert is related to infection risk which would be identified by a lower cut-point than the standard which is related to acute leukemias. A markedly abnormal high cut-point  $>30 \times 10^9/L$  is applied to flag leukocytosis (George 2012).

Albumin data is classed as unblinding and results will therefore only be available after unblinding.

Includes CRP and High Sensitivity (HS) CRP. Reference for marked abnormality criteria: Nehring, S.M.; Goyal, A.; Patel, B.C. (2020). StatPearls Publishing, web link: <https://www.ncbi.nlm.nih.gov/books/NBK441843/>.

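### Urinalysis is listed but not summarised, and for platelets, creatinine, eGFR and albumin the only laboratory-based abnormality counts start at CTCAE Grade 3

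*SAP*

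**What the plan says.** Protocol 2.3 names these among its safety topics of interest: "effects on the kidney, reductions in albumin and plasma proteins, drug-induced aseptic meningitis, and decreased platelet counts". Both documents carry an exploratory safety endpoint, worded in SAP Table 1-1 as "Change from Baseline in vital signs and laboratory results at scheduled assessments during the Treatment Period", running through the Run-Out Period.

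Protocol 9.4.1 plans laboratory evaluations analysed over time and states: "Possibly clinically significant treatment-emergent abnormalities will be listed and summarized by visit for each treatment group". It does not except urinalysis. The Schedule of Activities puts urinalysis in the same row as hematology and chemistry. Protocol Appendix 2 lists dipstick protein and blood, with microscopy if either is abnormal.

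SAP 5.6.6 treats the laboratory groups differently:

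- Urinalysis: "Urinalysis results will be listed for all study participants by treatment sequence". No table is described.
- Chemistry and hematology parameters "will be summarized by planned treatment sequence and periods and time point for both absolute values and changes from Baseline".
- Treatment-emergent marked abnormalities "will be summarized by clinical chemistry and hematology groups, planned treatment sequence and visit". SAP 8.1.1 bases these criteria on CTCAE version 5 Grade 3 or higher.
- High and low reference-range flags are derived for chemistry and hematology, but only for the participant listing.

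SAP 5.1.2 records three changes from the protocol: the Baseline for safety variables, the timing of the pain and fatigue scores, and the dropped placebo-based imputation. Urinalysis is not among them.

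**The concern.** The protocol names kidney effects, albumin reductions and platelet decreases as topics to watch, and the trial samples for them repeatedly. Yet the SAP's laboratory tables count a participant as abnormal only at a severe grade, and never for urine. In a trial with 20 participants per sequence, severe-grade cells may well be empty whether or not the drug has a milder effect. The reader of the report would then have means and extremes, adverse event terms that depend on the investigator's judgement, and pages of listings. There would be no direct comparison of how many participants in each arm moved from normal to abnormal.

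**Working it through.** There is no sample size, power or error-rate figure to reproduce. The check sets the planned outputs side by side and then illustrates what they can show.

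**1. Planned laboratory outputs (SAP 5.6.6 and 8.1.1)**

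| Parameter | Values and change by sequence | Laboratory-based count of abnormal results |
|---|---|---|
| Dipstick protein, blood | None | None |
| Platelets | Yes | Below 50 x 10^9/L |
| Creatinine | Yes | ">3.0 x ULN or >3.0 x" Baseline |
| eGFR | Yes, as a chemistry parameter | 29 mL/min/1.73 m2 or below |
| Albumin | Yes | Below 2 g/dL |

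**2. What the criteria leave uncounted** (starting values are illustrative)

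- Platelets falling from 250 to 50 x 10^9/L: (250 - 50)/250 = 80% fall, not counted, because the criterion is strictly below 50.
- eGFR falling from 90 to 30: (90 - 30)/90 = 67% fall, not counted by the eGFR criterion.
- Creatinine doubling from Baseline while at or below 3 x ULN: not counted by the creatinine criterion.
- New dipstick protein or blood of any degree: never counted from laboratory data.

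**3. Amount of urinalysis data without a summary**

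The Schedule of Activities places laboratory panels at Visits 3, 7, 11, 15, 19, 23, 27 and EOT/EW. Weekly assessments are taken before dosing, so Visit 3 precedes the first double-blind dose. That leaves 7 per participant: 7 x 60 = 420 at most, before the planned 25% dropout.

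**4. Illustration with assumed event rates**

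The documents give no rates, so every rate here is an assumption. The marked-abnormality table is by sequence, with n = 20 each.

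- Chance that a sequence shows no severe event, (1 - p)^20: p = 0.5% gives 0.91; 1% gives 0.82; 2% gives 0.67; 5% gives 0.36.
- Pooling Sequences 1 and 2 (n = 40) at p = 1%: 0.99^40 = 0.67. This pools 24-week and 12-week exposure.
- Lesser abnormality at 10%, 15% or 30%: 20p = 2, 3 or 6 participants expected per sequence, with a chance of at least one, 1 - (1 - p)^20, of 0.88, 0.96 or above 0.99.

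These figures show only that a lower-threshold table would probably have entries where the severe-grade table would often have none. They say nothing about power to detect a difference between arms.

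**5. How far adverse event reporting covers the topics**

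The kidney adverse event of focus (SAP 8.3) is a narrow search on acute renal failure terms. Platelets are not an adverse event of focus category (SAP 5.6.5). Protocol Appendix 2 withholds albumin results from sites until unblinding unless a safety alert requires clinical review, so investigators will generally not have an albumin value to report from.

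**6. Comparison within the SAP**

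For liver tests, SAP 5.6.9.5 counts participants at several thresholds (for example AST or ALT above 3, 5, 8, 10 and 20 x ULN) by treatment period and treatment group. Graded counts of this kind are already accepted for one organ system.

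**The case against.** The strongest reply is that lesser abnormalities do reach by-arm tables. Protocol Appendix 3 makes any clinically significant abnormal laboratory result an adverse event, urinalysis included, and Protocol 8.2.5 requires the investigator to review each report. SAP 5.6.2 then counts all TEAEs by treatment period and group, with tables by maximum intensity that include mild and moderate events. A reader might infer that an abnormality short of Grade 3 is counted nowhere; the documents do not support that. What stands is that this route depends on the investigator's judgement and is largely closed for albumin.

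Second, the continuous summaries report minimum and maximum (SAP 5.1), so an extreme platelet or creatinine value would show for its sequence and visit. A reader might infer that an excess on rozanolixizumab could not be seen by arm. That goes too far for these parameters: the missing item is the number of participants affected. The reply does not help urinalysis, which has no summary.

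Third, Protocol 9.4.1 sets no threshold for a possibly clinically significant abnormality and leaves detail to the SAP. Choosing Grade 3 is therefore not itself a departure from the protocol. Reducing urinalysis to a listing is, on a plain reading, and it goes unrecorded.

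Fourth, table shells are held in a separate document and could contain more. SAP 5.6.6 nevertheless distinguishes listing from summarising by laboratory group and assigns urinalysis to the listing.

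Finally, this is a 60-participant Phase 2a study with Safety Monitoring Committee review about every 3 months. That limits how much weight the point can carry.

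**Conclusion.** The point holds as a reporting gap of modest size. No laboratory-based by-arm count below Grade 3 is planned for the kidney, platelet and albumin topics that Protocol 2.3 names. It is clearest for dipstick protein and blood, where at most about 420 post-dose samples have no summary, and for albumin, where adverse event reporting can contribute little. For platelets, creatinine and eGFR it is a matter of adding participant counts to summaries that already exist. The conclusion rests on the text of the two documents. The event-rate figures are assumptions for illustration and carry none of it. The primary and secondary endpoints and the clinical management rules are unaffected.

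**What to change.** In SAP 5.6.6, add descriptive tables by treatment group and period:

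1. Shift from Baseline to worst post-Baseline category for dipstick protein and for dipstick blood, using the categories as reported.
2. Low/normal/high shifts for creatinine, platelets and albumin, using the reference-range flags already derived, and for eGFR using either a reference range or CTCAE grade.

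Keep the Grade 3 table as it is. State how samples map to periods. Under SAP Table 5-2 the laboratory Baseline precedes the Run-In, so the pre-dose Visit 3 sample belongs to the Run-In. The pre-dose samples at Visits 15 and 27 reflect the period just ended; SAP 5.1.1.2 says so only for efficacy, PK and PD data. If the sponsor prefers to keep urinalysis as a listing, SAP 5.1.2 should record that as a change from Protocol 9.4.1.

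The cost is a few standard tables, with no new sampling and no change to clinical rules. The downside is that some incidental abnormalities unrelated to treatment will be tabulated; the placebo columns put these in context.

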### **5.6.7 Vital Signs**

The following vital signs measurements will be assessed:

- Systolic and diastolic blood pressure
- Pulse rate
- Body temperature (oral, tympanic or axillary)
- Body weight

Vital signs assessment values and changes from Baseline will be summarized by planned treatment sequence, period, and time point where applicable, based on the SS-r. The time points summarized will be per Protocol Amendment 3. Therefore, any assessments completed by participants enrolled under any prior version of the protocol which are not required under Protocol Amendment 3, will be listed only.

Vital signs measurements will be listed by planned treatment sequence, period, and time point including changes from Baseline and details of abnormal values. Body weight will be listed only.

Treatment-emergent vital signs abnormalities defined as in Appendix 1, [Section 8.1.2](#) will be summarized by planned treatment sequence, period and by time point as applicable.

### **5.6.8 Electrocardiograms (ECG)**

The following ECG parameters will be reported:

- Heart rate
- PR interval

- RR interval
- QT interval
- QRS interval
- QTc interval (QT corrected for heart rate using Fridericia's formula [QTcF])

The individual measurements will be reported in the by-participant listings and will be presented by planned treatment sequence and time point. ECG findings will be listed separately.

### **5.6.9            Other Safety Variable(s)**

#### **5.6.9.1        Physical examination**

Study participants with abnormalities in the physical examination at Screening will be listed by planned treatment sequence for the SS-r including details of the abnormality.

#### **5.6.9.2        Neurological Examination**

In study participants who report severe and/or serious headache or suspected aseptic meningitis at the clinic visit, a full neurological examination (including fundoscopy) should be performed. Neurological examination and fundoscopy results will be listed by planned treatment sequence.

#### **5.6.9.3        Suicidal Risk Monitoring - C-SSRS**

Study participants will be monitored appropriately for suicidal ideation and behavior or any other unusual changes in behavior. Suicidality will be assessed by trained study personnel using the C-SSRS (Columbia University Medical Center, 2008). This scale will be used for screening as well as to assess suicidal ideation and behavior that may occur during the study. Collected C-SSRS data will be listed by planned treatment sequence for participants where suicidal ideation or behavior has been reported. Module of the questionnaire, time point, question and the associated response will be listed for all the visit days where this questionnaire is collected.

#### **5.6.9.4        Assessment of Tuberculosis and Tuberculosis Risk Factors**

TB will be evaluated via various assessments as specified below during the study. Findings for TB assessment performed during PE after screening will be reported as AEs. No separate TB listing or table will be produced for PE TB assessment.

The TB questionnaire will not be reported. TB assessment by IGRA will be reported together with other laboratory parameters.

No separate TB listing or table will be produced for IGRA TB assessment.

TB assessment by chest X-ray or other assessments will not be reported.

IGRA test conversions should be reported as AEs as described in the protocol. The AE term would need to be updated with final diagnosis once available.

No specific listing will be provided for test conversion.

